**Table 8: Overview of Analysis of Laboratory Data for RCP (SS)**

Type of Analysis	Assessment Performed	Additional Notes
Actual value and change from Baseline	X	
Abnormal laboratory values (with respect to normal range)	X	
Shift analysis of abnormality compared to Baseline	X	
Liver function abnormality	X	
Box plots	X	ALT, AST, creatinine, glucose, hematocrit, hemoglobin, lymphocytes neutrophils, leukocytes, and platelets

The treatment group display convention is “Ravulizumab, Placebo”, and the definition of baseline values is “Last nonmissing value prior to first RCP study drug infusion.”

Abbreviations: ALT = alanine aminotransferase; AST = aspartate aminotransferase; RCP = Randomized Controlled Period; SS = Safety Set

#### 5.6.4. Vital Signs

The analysis of the following vital signs will be summarized descriptively: systolic blood pressure (mmHg), diastolic blood pressure (mmHg), heart rate (beats/min), respiratory rate (breaths/min), weight (kg), and temperature (°C).

If there are multiple records of vital sign measurements at Baseline or post-Baseline Visits, the last record will be used. The following analyses will be performed:

- Actual vital sign measurements, baseline values, and changes from Baseline will be summarized using descriptive statistics (mean, SD, etc.) for each scheduled study visit.
- The number (%) of participants meeting the potentially clinically significant abnormality criteria (Table 9) at least once during the RCP will be provided.

**Table 9: Potentially Clinically Significant Abnormality Criteria for the Vital Signs**

Vital Sign Measurement	Criteria
Systolic blood pressure	< 90, > 140, > 160
Diastolic blood pressure	< 50, > 90, > 100
Heart rate	< 60, > 100
Respiratory rate	< 12, > 20
Weight	Decrease of $\geq 7\%$ from Baseline; increase of $\geq 7\%$ from Baseline
Temperature	> 38.0, < 36.0

Table 10 provides an overview of the analyses of the vital sign data for different periods, underlying analysis sets, treatment group display convention, the definition of baseline values, and analyses of the vital sign data. An “X” in the table represents that an analysis will be performed for the period.

**Table 10: Overview of Analysis of Vital Sign Data for RCP (SS)**

Type of Analysis	Assessment Performed
Actual value and change from Baseline	X
Potentially clinically significant abnormality criteria	X

The treatment group display convention is “Ravulizumab, Placebo”, and the definition of baseline values is “Last nonmissing value prior to first RCP study drug infusion.”

Abbreviations: RCP = Randomized Controlled Period; SS = Safety Set

### 5.6.5. Electrocardiogram

The analysis of the following ECG measurements will be summarized descriptively: heart rate (beats/min), PR interval (msec), QRS duration (msec), RR interval (msec), QT interval (msec), corrected QT interval by Fridericia (QTcF; msec), and overall interpretation.

If there are multiple records of ECG measurements at Baseline or post-Baseline Visits, the last record will be used. The following analyses will be performed:

- Actual ECG measurements, baseline values, and changes from Baseline will be summarized using descriptive statistics (mean, SD, etc.) for each scheduled study visit
- The number (%) of participants with abnormal ECG findings (normal, abnormal – not clinically significant, and abnormal – clinically significant).
- The number (%) of participants meeting the potentially clinically significant abnormality criteria (Table 11) for QT and QTcF at least once during the RCP will be provided.

**Table 11: Potentially Clinically Significant Abnormality Criteria for QT and QTcF**

ECG Measurement	Criteria
QT, QTcF absolute value	> 450, > 480, > 500
QT, QTcF absolute value	> 450 to ≤ 480, > 480 to ≤ 500, > 500
QT, QTcF change from Baseline	> 30, > 60
QT, QTcF change from Baseline	> 0 to ≤ 30, > 30 to ≤ 60, > 60

Note: Maximum post-Baseline value or maximum change from Baseline will be used for these evaluations.

Table 12 provides an overview of the different periods, underlying analysis sets, treatment group display convention, the definition of baseline values, and analyses of ECG data. An “X” in the table represents that an analysis will be performed for the period.

**Table 12: Overview of Analysis of ECG Data for RCP (SS)**

Type of Analysis	Assessment Performed
Actual value and change from Baseline	X
Abnormal ECG findings	X
Potentially clinically significant abnormality criteria for QT and QTcF	X

The treatment group display convention is “Ravulizumab, Placebo”, and the definition of baseline values is “Last nonmissing value prior to first RCP study drug infusion.”

Abbreviations: ECG = electrocardiogram; QTcF = corrected QT interval by Fridericia; RCP = Randomized Controlled Period; SS = Safety Set

**5.6.6. Physical Examination**

Details will be provided in a listing.

**5.6.7. Neurological Examination**

Details will be provided in a listing.

**5.6.8. Columbia-Suicide Severity Rating Scale**

The following C-SSRS categories with a yes/no binary response have been re-ordered from the actual scale to facilitate the definitions of the composite and comparative endpoints and enable clarity in presenting the results.

**Table 13: C-SSRS Categories for Reporting**

Category No.	Category
1	Wish to be Dead
2	Nonspecific Active Suicidal Thoughts
3	Active Suicidal Ideation With Any Methods (Not Plan) Without Intent to Act
4	Active Suicidal Ideation With Some Intent to Act, Without Specific Plan
5	Active Suicidal Ideation With Specific Plan and Intent
6	Preparatory Acts or Behavior
7	Aborted Attempt
8	Interrupted Attempt
9	Actual Attempt (Nonfatal)
10	Completed Suicide

Abbreviations: C-SSRS = Columbia-Suicide Severity Rating Scale; No. = number

In addition, the response to the “Self-injurious behavior without suicidal intent (not suicide-related)” question will also be summarized.

Table 14 provides the definitions for the composite endpoints based on the categories provided in Table 13.

**Table 14: Composite Endpoints Based on C-SSRS**

Endpoint	Description
Suicidal ideation	A “yes” answer to any of the 5 suicidal ideation questions (Categories 1-5) on the C-SSRS.
Suicidal behavior	A “yes” answer to any of the 5 suicidal behavior questions (Categories 6-10) on the C-SSRS.
Suicidal ideation or behavior	A “yes” answer to any 1 of the 10 suicidal ideation and behavior questions (Categories 1-10) on the C-SSRS.

The following analyses will be performed:

- The number and percentage of participants who experience an event at Baseline (“Lifetime” and “past 12 months,” separately) and at least once during the treatment period will be summarized by the treatment group for
  - Each of the 3 composite endpoints in [Table 14](#)
  - The self-injurious behavior without suicidal intent
- A shift tabulation from Baseline (“Lifetime” and “past 12 months,” separately) will be produced by treatment group during the RCP against the 3 composite endpoints for each of the 3 following groupings:
  - No suicidal ideation or behavior,
  - Composite endpoint of suicidal ideation, and
  - Composite endpoint of suicidal behavior. Each participant is counted once in 1 cell only for each of the 2 tabulations. Participants with both suicidal ideation and suicidal behavior are included in the suicidal behavior category for the shift analysis.

### 5.6.9. Coronavirus Disease 2019 Exposure

Details will be provided in a listing.

## 5.7. Other Analyses

### 5.7.1. Pharmacokinetic Analyses

Individual serum concentration data for all participants in PKAS will be summarized descriptively. Descriptive statistics (mean, SD, coefficient of variation [CV], median, minimum, maximum, geometric mean, and geometric %CV) will be calculated for serum concentration data at each sampling time, as appropriate. Graphs of mean serum concentration-time profiles will be constructed. Graphs of serum concentration-time profiles for individual participants may also be provided.

### 5.7.2. Pharmacodynamic Analyses

PD analyses will be performed for all participants in PDAS. Descriptive statistics will be presented for all ravulizumab PD endpoints at each sampling time. The PD effects of ravulizumab will be evaluated by assessing the absolute values, changes, and percentage changes from Baseline in free C5 serum concentrations over time, as appropriate.

Assessments of ravulizumab PK/PD relationships may be explored using data from this study or in combination with data from other studies.

### **5.7.3. Biomarker Assessments**

Analysis of Neurofilament Light Chain (NfL) concentration can be found in Section 5.4.2.2. All other biomarkers may be analyzed by treatment and visits.

### **5.7.4. Immunogenicity**

The number and percentage of participants developing confirmed positive ADAs and anti-drug neutralizing antibodies, where applicable, will be summarized by treatment group and visit. ADA titer values will be listed.

### **5.7.5. Subgroup Analyses**

#### **5.7.5.1. Subgroup Analyses for Adverse Events**

The TEAEs during the RCP will be summarized for the following subgroups (no p-value will be produced for these subgroup analyses):

- Sex
- Race
- Region
- Age category (< median, ≥ median)
- Baseline weight category (< median, ≥ median)

#### **5.7.5.2. Subgroup Analyses for Laboratory Data**

The abnormality criteria for liver function laboratory values (Table 7) will be summarized for the following subgroups; no p-value will be produced for these subgroup analyses:

- Stable use of riluzole at baseline (yes, no)
- Stable use of edaravone at baseline (yes, no)

## **5.8. Interim Analyses**

An unblinded interim analysis is planned to assess futility when approximately 33% of planned 354 participants complete Week 26. The interim analysis will be conducted by an IDMC. Details have been described in a separate IAP document.

### **5.8.1. Data Monitoring Committee**

The safety and efficacy data of this study will be monitored by an IDMC composed of external physicians and a statistician who have expertise in both the field of ALS and clinical trial conduct and with no direct relationship to the study. An independent statistical center will perform all statistical analyses presented to the IDMC. The IDMC will independently evaluate safety and efficacy data from the study periodically and at prespecified enrollment-dependent time points. The IDMC will make recommendations regarding study modification or continuation based on their review and in accordance with the agreed-upon IDMC charter. To maintain study integrity and prevent the potential introduction of bias, all study team members

will remain blinded until the final analysis of the RCP is conducted. Details of this process are documented in the IDMC charter.

## 6. SUPPORTING DOCUMENTATION

### 6.1. Appendix 1: Demographics, Baseline Characteristics, Inclusion/Exclusion Criteria, Protocol Deviations, Medical/Surgical History, Prior/Concomitant Medication

#### 6.1.1. Demographics and Other Baseline Characteristics

The following demographics and baseline characteristics (including ALS disease history) will be summarized using the FAS by treatment group and overall. No statistical test will be performed for homogeneity among treatment groups. The continuous data will be summarized with descriptive statistics (number of participants with nonmissing data [n], mean, SD, minimum, and maximum), and the categorical data will be summarized with the number of participants with non-missing data (n) and percentages (%) for each category. The denominator will not include the missing data for percentage calculation.

##### 6.1.1.1. Demographics

- Sex (male, female, undifferentiated, unknown) – n (%)
- Race – n (%) (as characterized in Section IV of the FDA guidance titled, “Collection of Race and Ethnicity Data in Clinical Trials”); [Table 15](#) provides both the primary and the detailed categories with mapping per the FDA guidance. The primary race category will be used for subgroup analysis.
- Ethnicity – n (%) (as characterized in Section IV of the FDA guidance titled, “Collection of Race and Ethnicity Data in Clinical Trials”); [Table 16](#) provides both the primary and the detailed categories with mapping per the FDA guidance.
- Age (years) at screening – descriptive statistics
- Age category (< 45, 45 to < 65, ≥ 65 years) – n (%)
- Weight (kg) – descriptive statistics
- Weight category (< 40, ≥ 40 to < 60, ≥ 60 to < 100, ≥ 100 kg) – n (%)
- Height (cm) measured at screening – descriptive statistics
- Body mass index (BMI) (kg/m^2) – descriptive statistics
- BMI categories (<18.5, ≥ 18.5 to < 25, ≥ 25 to < 30, ≥ 30) – n (%)

**Table 15: Race Categories**

Primary (section IV.D of FDA guidance document)	Detailed (section IV.E of FDA guidance document and as recorded on the case report form)
American Indian or Alaska Native	American Indian or Alaska Native
Asian	Asian Indian, Chinese, Filipino, Japanese, Korean, Vietnamese, Other Asian
Black or African American	Black or African American

**Table 15: Race Categories**

Primary (section IV.D of FDA guidance document)	Detailed (section IV.E of FDA guidance document and as recorded on the case report form)
Native Hawaiian or Other Pacific Islander	Native Hawaiian, Guamanian or Chamorro, Samoan, Other Pacific Islander
White	White

**Table 16: Ethnicity Categories**

Primary (section IV.D of FDA guidance document)	Detailed (section IV.E of FDA guidance document and as recorded on the case report form)
Hispanic or Latino	
 
• Mexican, Mexican American, Chicano/a
 
• Puerto Rican
 
• Cuban
 
• Another Hispanic, Latino/a or Spanish origin
 

Not Hispanic or Latino	Not of Hispanic, Latino/a, or Spanish origin
Not reported	Not reported
Unknown	Unknown

Age, weight, and BMI will be reported based on the most recent data on or before Day 1 (the first study drug infusion).

**6.1.1.2. Baseline Characteristics**

Table 17 provides the list of baseline characteristics to summarize along with the type of summary.

**Table 17: Baseline Characteristics**

Baseline Characteristics	Definition
Time (months) since first muscle weakness at Screening – descriptive statistics	$12 \times [\text{date of informed consent} - \text{date of first muscle weakness}] / 365.25$ (rounded to nearest 1)
Time (months) since first muscle weakness at Baseline – descriptive statistics	$12 \times [\text{date of Day 1} - \text{date of first muscle weakness}] / 365.25$ (rounded to nearest 1)
Time since first muscle weakness at Baseline category – n (%)	< 12, 12 to ≤ 24, > 24 months
Time (months) since initial diagnosis of ALS at Baseline	$12 \times [\text{date of Day 1} - \text{date of diagnosis}] / 365.25$ (rounded to nearest 1)
Time (months) since first muscle weakness to the initial diagnosis of ALS – descriptive statistics	$12 \times [\text{date of diagnosis} - \text{date of first muscle weakness}] / 365.25$ (rounded to nearest 1)
Site of muscle weakness onset – n (%)	Bulbar, other
El Escorial Diagnostic Criteria – n (%)	Possible; Probable; Probable, Laboratory-supported; Definite
Type of ALS disease – n (%)	Sporadic, Familial
ALS gene mutation – n (%)	C9ORF72, SOD1, TDP43, FUS, No known mutation, Other

**Table 17: Baseline Characteristics**

Baseline Characteristics	Definition
Ventilation use at Screening – n (%)	
 
PAV use
 
PAV use for <math>\geq 22</math> hours for <math>\geq 7</math> consecutive days
 
NIV use
 
NIV use for <math>\geq 22</math> hours for <math>\geq 10</math> consecutive days
 

King’s ALS Clinical Staging at Baseline – n (%)	Stage 1, Stage 2, Stage 3, Stage 4
King’s ALS Clinical Staging assessment, region affected – n (%)	Bulbar, Upper extremity, Lower extremity
King’s ALS Clinical Staging assessment, nutritional status – n (%)	
 
Lost > 10% from predisease weight
 
Feeding tube needed
 

King’s ALS Clinical Staging assessment, evidence of respiratory failure – n (%)	NIV use, SVC < 50% predicted, SVC 50% to < 80% predicted with respiratory symptoms, None of the above
Dependence on mechanical ventilation – n (%)	Yes, No
Type of dependence on ventilation – n (%)	
 
Unable to lie flat (supine) without it
 
Unable to sleep without it
 
Daytime use > 6 hours per day for > 3 days per week
 

Stable riluzole or edaravone at Screening – n (%)	
 
Riluzole
 
Edaravone
 
Riluzole, not edaravone
 
Edaravone, not riluzole
 
Both riluzole and edaravone
 
No riluzole or edaravone
 

Stable riluzole or edaravone at any time prior to Screening – n (%)	
 
Riluzole
 
Edaravone
 
Riluzole, not edaravone
 
Edaravone, not riluzole
 
Both riluzole and edaravone
 
No riluzole or edaravone
 

Time (months) since the first use of riluzole at baseline – descriptive statistics	$12 \times [\text{date of Day 1} - \text{date of first riluzole use}] / 365.25$ (rounded to nearest 1)
Time (months) since the first use of edaravone at Baseline – descriptive statistics	$12 \times [\text{date of Day 1} - \text{date of first edaravone use}] / 365.25$ (rounded to nearest 1)
ALSFRS-R total score at Screening and Baseline – descriptive statistics	
ALSFRS-R total score at Screening categories – n (%)	< 34, 34 to 38, > 38 to 40, > 40
ALSFRS-R total score at Baseline categories – n (%)	< 34, 34 to 38, > 38 to 40, > 40
Prestudy monthly ALSFRS-R progression rate at Screening – descriptive statistics	As collected on the case report form
Prestudy monthly ALSFRS-R progression rate at Day 1 – descriptive statistics	$[\text{48-ALSFRS-R total score at Day 1}] / \text{Time (months) since first muscle weakness at Day 1}$ – descriptive statistics
Progression rate of ALSFRS-R at Screening categories – n (%)	< -1, -1 to < -0.7, -0.7 to < -0.5, -0.5 to < -0.3, > -0.3
Progression rate of ALSFRS-R at Baseline categories – n (%)	< -1, -1 to < -0.7, -0.7 to < -0.5, -0.5 to < -0.3, > -0.3

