#### Type of Patient and Disease Characteristics

2. A diagnosis of ALS, defined as meeting the possible, laboratory-supported probable, probable, or definite criteria for a diagnosis of ALS according to the revised World Federation of Neurology El Escorial criteria. Patients diagnosed with either sporadic or familial ALS are eligible for enrollment.
3. ALS onset, defined as time of onset of first muscle weakness (eg, limb weakness, dysarthria, dysphagia, shortness of breath),  $\leq 36$  months from the Screening Visit.
4. Prestudy ALSFRS-R progression between disease onset and screening of  $-0.3$  points per month or worse (calculated by ALSFRS-R total score decline from 48 divided by the months since onset of ALS symptoms).
5. Upright SVC  $\geq 65\%$  predicted at Screening.
6. Vaccinated against *N. meningitidis* within 3 years prior to, or at the time of, initiating ravulizumab. Patients who initiate study drug treatment less than 2 weeks after receiving a meningococcal vaccine must receive appropriate prophylactic antibiotics until 2 weeks after the vaccination.
7. Patients who enter the study receiving standard of care for ALS (ie, riluzole and/or edaravone), either in combination or monotherapy, must be on a stable dosing regimen of adequate duration prior to screening with no plan to discontinue or to change the dose during the study period as follows:
  - If a patient who enters the study is receiving riluzole, the patient must have been on a stable dose of riluzole for  $\geq 30$  days prior to Day 1.
  - If a patient who enters the study is receiving edaravone, the patient must have initiated edaravone  $\geq 60$  days (2 treatment cycles) prior to Day 1.

**Note:** Patients who are naïve to ALS therapies or have not taken approved ALS therapies for at least 30 days before screening are allowed to enroll.

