**Figure 2: Participant Disposition Flowchart**

### 5.3. Primary Estimand and Analysis

The primary endpoint for this study is based on ALSFRS-R. It is a validated instrument for evaluating the levels of the physical functional status of patients with ALS in 4 areas, including bulbar, gross motor activity, fine motor activity, and respiratory functions. The scale includes 12 functional items, and each item is rated on a 0 to 4 scale, with a maximum total score of 48. A higher score indicates greater retention of function. The ALSFRS-R assessment schedule is provided in the Schedule of Activities in the protocol. If a participant is unable to attend the scheduled onsite visit, the ALSFRS-R can be assessed via a phone call by the Investigator or trained designee.

A joint rank analysis (referred to as CAFS) recommended in the [Food and Drug Administration \(FDA\) guidance document on ALS, 2019](#), which combines deaths and ALSFRS-R, will be performed for the analysis of the primary endpoint. This analysis will be conducted based on the FAS.

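### SAP Table 17: the Day 1 progression rate is never negative but its Baseline classes have negative cut-points, so all patients fall in one class; and exactly -0.3 has no class

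*SAP*

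**What the plan says.** SAP Section 6.1.1.2, Table 17, summarises the pre-study rate of ALSFRS-R decline at two time points, first with descriptive statistics and then in classes.

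- Screening rate: "As collected on the case report form". No formula or sign is given.
- Day 1 rate, in the row "Prestudy monthly ALSFRS-R progression rate at Day 1": the numerator is "48-ALSFRS-R total score at Day 1" and the denominator is "Time (months) since first muscle weakness at Day 1".
- Classes, identical in the Screening and Baseline rows: "< -1, -1 to < -0.7, -0.7 to < -0.5, -0.5 to < -0.3, > -0.3".

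The protocol states the entry rule twice, with opposite signs. Inclusion criterion 4 (Section 5.1) requires "Prestudy ALSFRS-R progression between disease onset and screening of" -0.3 points a month or worse, so the boundary itself is eligible. Section 3.2.1 gives the threshold as 0.3 and the formula as 48 minus the Screening score, over months since onset.

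**The concern.** Table 17 takes its Day 1 formula from the positive convention and its classes from the negative one, and no text in the SAP reverses the sign. The progression criterion is the trial's enrichment rule, and these rows describe how fast the enrolled patients had been declining. A Baseline row with all patients in one class carries no information, and that class is the one intended for decline slower than the entry limit.

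The second defect sits at the same limit. The fourth class stops short of -0.3 and the fifth starts above it. The other shared cut-points (-1, -0.7, -0.5) each belong to exactly one class, so the gap looks like an oversight. A programmer who noticed only the sign problem and reversed it would then have to decide, without instruction, where to put patients at the boundary.

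**Working it through.** The plan states no figure to reproduce here, so the check is of the logic.

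**Inputs**
- ALSFRS-R is scored "with a maximum total score of 48" (SAP Section 5.3), so 48 minus the score lies between 0 and 48.
- Onset is at most 36 months before Screening (inclusion criterion 4's neighbour, criterion 3), and Screening lasts up to 4 weeks. Months at Day 1 therefore run to about 37.
- "Time (months) since first muscle weakness at Baseline" is rounded to whole months in Table 17. I assume the Day 1 rate uses this rounded value.
- I take the Baseline class row to apply to the Day 1 rate, the only baseline rate that the table defines.

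**Step 1: sign.** Rate = (48 - score) / months. The numerator is at least 0 and the denominator is positive, so the rate is at least 0, and any such value exceeds -0.3. Example: score 38 at 15 months gives (48 - 38)/15 = +0.67, which is classed `> -0.3`. With the sign reversed it is -0.67, in `-0.7 to < -0.5`.

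**Step 2: enumeration.** Scores 0 to 48 (49 values) and months 1 to 37 (37 values) give 49 x 37 = 1,813 pairs. Each was classified in exact fractions.

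| Class | Formula as written | Sign reversed |
|---|---|---|
| `< -1` | 0 | 1,073 |
| `-1 to < -0.7` | 0 | 228 |
| `-0.7 to < -0.5` | 0 | 133 |
| `-0.5 to < -0.3` | 0 | 148 |
| `> -0.3` | 1,813 | 228 |
| No class | 0 | 3 |
| Total | 1,813 | 1,813 |

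These are counts of possible value pairs, not expected numbers of patients.

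**Step 3: boundary.** With the sign reversed, the three unclassified pairs are those equal to exactly -0.3:
- score 45 at 10 months: -3/10
- score 42 at 20 months: -6/20
- score 39 at 30 months: -9/30

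Ending the fourth class at `<= -0.3` leaves none unclassified. In the Baseline row the two defects do not operate together: as written, no value is negative, so -0.3 is never reached; after the sign is corrected, the gap becomes active.

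**Step 4: where the rate is used.** It is not a covariate in the CAFS analysis of covariance (SAP 5.3.2), the ALSFRS-R repeated-measures model (5.3.3.1.2), the Cox model for VAFS (5.4.1.1.2) or the SVC model (5.4.1.2.2). It is not among the subgroups in 5.7.5. The sample size (SAP Section 3) rests on an assumed on-study slope, not on this derived variable.

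**The case against.** The strongest reply is that the intent can be recovered. The protocol uses both signs for one quantity, four empty classes would be obvious at programming, and output specifications sit in a separate data presentation plan that is not available here. The Day 1 descriptive statistics remain readable as points lost per month, and failures of entry criteria are summarised separately (SAP 6.1.2). The trial had also met its futility criterion, so p-values and intervals are descriptive only (SAP 5.1).

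All of that limits the consequence. It does not remove the error: the rule as written gives an uninformative row, and the recoverable intent settles the sign but not where -0.3 belongs.

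Three stronger readings are tempting and are not supported.

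- *Every patient is misclassified.* Every patient lands in one class, but some may belong there. Score 42 at 20 months at Screening gives 6/20 = 0.300, which is eligible. An unchanged 42 at 21 months on Day 1 gives 6/21 = 0.286, which is truly slower than 0.3.
- *The table says that nobody met the entry rate.* Entry is judged at Screening, and the Baseline row does not report eligibility.
- *The Screening row fails in the same way.* Its sign is not stated. Criterion 4 uses -0.3, so the form may record negative values, and the row may then work except at the boundary.

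**Conclusion.** The point holds as a minor error in a stated derivation rule.

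- **Sign:** in the Baseline row, all 1,813 enumerated pairs fall in `> -0.3`. This follows from the range of the scale and does not depend on the grid or on rounding.
- **Boundary:** exactly -0.3 has no class in either row. The gap bites only where values are negative. It is small: 3 of the 1,813 pairs with the sign reversed. That count assumes whole months, which the SAP states for time since onset at Baseline but not for the rate on the case report form.
- **Reach:** descriptive baseline reporting only. Nothing in the documents carries the error into an efficacy or safety comparison.

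**What to change.** Use one sign convention for both time points, and close the boundary in both category rows. Either of these does it:

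- Define the Day 1 rate as (ALSFRS-R total - 48) / months, confirm that the Screening rate from the case report form has the same sign (or derive it the same way), and write the last two classes as `-0.5 to <= -0.3` and `> -0.3`.
- Keep the positive formula, confirm that the Screening value is positive, and use the mirrored classes `> 1`, `> 0.7 to 1`, `> 0.5 to 0.7`, `0.3 to 0.5` and `< 0.3`.

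Both changes are needed: correcting the sign alone would leave eligible patients at -0.3 unclassified. The cost is a few lines in Table 17 (two category rows, plus the formula row under the first option), the matching table specification, and one check of how the form records the Screening rate. No analysis has to be re-planned.
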